6.7.2 Safety review committee

Specific dose escalation meetings will be conducted every 4-6 weeks, or when 3 patients have completed the 28-day DLT window, whichever is earlier. These will be to determine if the dose level has been tolerated by the patients and that it is safe to escalate the dose to the next level. Dose escalation decisions will be led by the SRC which will consist of:

- Chief Investigator or delegate
- Principal Investigator or delegate from each investigational site

- RM CTU operations manager or delegate
- Trial Statistician
- Senior Phase 1 trial clinician (who is not CI/PI)
- Senior melanoma trial clinician (who is not CI/PI)
- Chairperson (must be independent of the Investigators/institution)

Further internal or external experts may be included by the SRC as necessary.

Part B, the dose expansion stage, is being conducted in two large and experienced melanoma units who have also worked extensively together on trials on multiple previous occasions. The above described SRC will also convene at regular intervals (at least quarterly) to review the accumulating safety data from the trial during the dose expansion stage; more frequent meetings will be dictated by availability and severity of on-going safety information. They will meet (teleconference) within a week of any grade 4 toxicities or death, regardless of whether thought attributable to CCT3833 or not.

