6.8 Dose escalation decisions

An SRC meeting will be triggered when three patients have had the opportunity to complete the first cycle of treatment. The safety data including a list of DLTs and all AEs will be reviewed, along with all other available data (including PK analyses from at least two subjects), in order to make the decision. When sufficient data are available to assess the existing cohort, the next dose level will be assigned according to the following:

- Proceed with dose escalation: If the data is available from three patients who have been treated in a cohort and no DLTs have been observed at that dose level, then dose escalation can be considered.
- Expand the cohort to further explore the dose level: If the data is available from three patients who have been treated in a cohort and one DLT has been observed at that dose level, then the cohort will be expanded to include six patients.
- De-escalate the dose: If two DLTs have been observed at any dose level, the dose will be de-escalated to either the previous dose level (expanding to include up to six patients) or an intermediate dose level will be explored. If the previous dose level already included a cohort of six patients then this will be identified as the MTD.
- Explore different dosing schedules or formulations: If the daily continuous dosing treatment schedule is not tolerated, then the frequency of dosing for subsequent patients may be reduced. Dose escalation will continue at the reduced schedule.
- Stop the dose escalation phase of the study.

The decisions of the SRC on the next dose level and/or dosing schedules will be documented and provided to the Investigators prior to dosing any new patients.

The RP2D to be further evaluated in Part B (expansion phase) will be determined by the SRC based on the MTD and observed safety profile, PK and PD data. During the expansion phase, the SRC will continue to monitor safety and will agree any action needed to refine the dose or dosing schedule.

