9 ASSESSMENT OF SAFETY

9.1 Adverse event definitions

9.1.1 Adverse events

An adverse event (AE) is any untoward, undesired or unplanned occurrence in a patient administered an IMP, a comparator product or an approved drug. An AE can be a sign, symptom, disease, and/or laboratory or physiological observation that may or may not be related to the CCT3833 or comparator.

An AE includes but is not limited to those in the following list:

- A clinically significant worsening of a pre-existing condition. This includes conditions that may resolve completely and then become abnormal again.
- AEs occurring from an overdose of an IMP, whether accidental or intentional.
- AEs occurring from lack of efficacy of an IMP, for example, if the Investigator suspects that a drug batch is not efficacious or if the Investigator suspects that the IMP has contributed to disease progression.

Other reportable events that must be treated as AEs are listed below:

- Pregnancy exposure to the IMP. Any pregnancy occurring in a patient or a patient's partner during treatment with an IMP or occurring within 6 months of the last IMP administration must be reported to the RM-CTU in the same timelines as an SAE. These should be reported even if the patient is withdrawn from the trial.
- Overdose or inadvertent or accidental exposure to an IMP with or without an AE
- Any AE that could be related to the protocol procedures, and which could modify the conduct of the trial.

Underlying disease - Any event(s) considered related to the underlying disease do not require reporting.

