9.1.2 Serious adverse events

A serious adverse event (SAE) is any AE, regardless of dose, causality or expectedness, that:

- results in death.
- is life-threatening.
- requires in-patient hospitalisation or prolongs existing in-patient hospitalisation (some hospitalisations are exempt from SAE reporting – see section 9.2.1).
- results in persistent or significant incapacity or disability.
- is a congenital anomaly or birth defect.
- is any other medically important event.

For screening failures, SAEs will be reported to the RM-CTU from the date of consent until the date the patient is confirmed as ineligible. For eligible patients, SAE and AE collection and monitoring commences from the time the patient gives their written consent to participate in the trial and continues for 28 days after the last administration of the IMP.

Follow-up of AEs with a causality of possibly, probably or highly probably related to the IMP will continue until the events resolve, stabilise or the patient starts another anti-cancer therapy.

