9.2.1 Events exempt from being reported as SAEs

Events specified in this section do not require reporting as SAEs in this trial, unless hospitalisation is prolonged for any reason and then an SAE form must be completed. The events must still be recorded in the appropriate section of the case report form (eCRF).

Underlying disease - Any events considered related to the underlying disease, such as disease progression, do not require SAE reporting.

Elective admissions

Elective admissions to hospital for procedures which were planned and documented in the medical records at the time of consent are not SAEs, and do not require SAE reporting. Hospitalisation for administration of the IMP, or to facilitate study procedures such as pharmacokinetic sampling according to the trial protocol is also exempt from being reported as an SAE.

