11.2 Completion of the electronic case report form

The Investigators are responsible for ensuring the accuracy, completeness, clarity and timeliness of the data reported in the eCRFs.

Only the Investigator and those personnel who have completed the Study Team Responsibilities Delegation Log as authorised by the PI, should enter or change data in the eCRFs. All protocol required investigations must be reported in the eCRF. The Investigators must retain all original reports, traces and images from these investigations for future reference. The data will be entered in a clinical trials database (Macro V4).

The eCRF will be signed electronically by the Investigator or by an authorised staff member. Study specific information will be entered into an eCRF on a regular basis (ideally after each patient visit). Data that are derived should be consistent with the source documents or the discrepancies should be explained. All eCRF data should be anonymous, ie identified by study patient number only.

Once data has been entered by the site personnel on the eCRF, the data will be reviewed and checked for error and inconsistencies by data management staff at the CTU.

Once the patient is 'off study' and the eCRF has been fully completed, the Investigator must provide a signature to authorise the complete subject data.

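### No reporting rule secures the Part B commitment that the SRC meets within a week of any grade 4 toxicity or death, and 9.1.1 contradicts 9.2.1 and 9.3 on disease-related events

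*Combined protocol and SAP*

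**What the plan says.** Section 6.7.2 gives the SRC two kinds of Part B meeting. The routine one: "The above described SRC will also convene at regular intervals (at least quarterly) to review the accumulating safety data". The urgent one: "They will meet (teleconference) within a week of any grade 4 toxicities or death, regardless of whether thought attributable to CCT3833 or not". The membership list includes the chief investigator, the RM-CTU operations manager and the "Principal Investigator or delegate from each investigational site".

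Section 9.1.2 opens its definition with "A serious adverse event (SAE) is any AE, regardless of dose, causality or expectedness, that" and then lists six criteria. Death, threat to life and a residual category of medical importance are among them; a CTCAE grade is not. Section 9.2 sends every SAE to RM-CTU within 24 hours of the site learning of it.

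Section 9.2.1 then makes an exception: "Any events considered related to the underlying disease, such as disease progression, do not require SAE reporting". The exception lapses if a hospital stay is prolonged, and exempt events must still go into the case report form. Section 9.1.1 is wider: "Any event(s) considered related to the underlying disease do not require reporting". Section 9.3 requires all AEs to be recorded in the eCRF, and 11.2 sets the pace: "Study specific information will be entered into an eCRF on a regular basis (ideally after each patient visit".

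For Part A, 6.7.2 schedules SRC meetings every 4 to 6 weeks, or earlier once three patients have completed the 28-day window. Section 6.8 adds: "An SRC meeting will be triggered when three patients have had the opportunity to complete the first cycle of treatment". No urgent SRC trigger is written for Part A.

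**The concern.** The urgent trigger deliberately ignores attribution, while the route that would feed it is filtered by attribution and by seriousness. If a site judges a death or a grade 4 event to be due to disease, 9.2.1 lifts the 24-hour duty. If a grade 4 laboratory result meets no seriousness criterion, the duty never arises. In both cases the site can follow section 9 to the letter and the SRC may still not hear within the week that 6.7.2 promises.

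The conflict over recording is a separate matter. Safety and tolerability is a primary endpoint in both parts (10.3), and 10.3.1 asks for AE tables that separate related from unrelated events. If one site follows 9.1.1 and another follows 9.2.1 and 9.3, the unrelated events will be collected unevenly.

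**Working it through.** The plan states no figure on this point, and no sample size or error rate depends on it. The check sets each route by which the SRC could learn of an event against the seven-day limit.

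| Route | Source | Time limit | Secures 7 days? |
|---|---|---|---|
| SAE report to RM-CTU | 9.2 | 24 hours | Yes, for events not exempt |
| Management group call | 6.7.1, described with Part A | usually 14 days | No |
| eCRF entry | 9.3, 11.2 | none fixed | No |
| Routine Part B SRC meeting | 6.7.2 | at least quarterly, about 91 days | No |

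Part B visits (8.2.2.1) fall on Cycle 1 Day 1, Cycle 1 Day 15 and Cycle 2 Day 1, then monthly if there is no DLT. The gaps are 14, 14 and then 28 days, so eCRF entry after each visit would not guarantee seven days either.

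Only the SAE report is fast enough. Which trigger events can fall outside it?

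1. **Events judged disease-related.** 9.2.1 exempts them unless hospitalisation is prolonged. It names progression and does not mention death; that it covers disease-related deaths is an inference from its reference to any events. A grade 4 event called disease-related is exempt on the same terms, even if it is serious.
2. **Non-serious grade 4 events.** Grade is not a criterion in 9.1.2. Table 15, footnote G requires a repeat blood count after grade 4 neutropenia or thrombocytopenia, but no notification.
3. **Deaths in survival follow-up.** AE and SAE collection ends 28 days after the last dose (9.1.2), apart from drug-related SAEs that come to light later (9.2). Part B survival follow-up runs for 12 months by telephone (8.2.4). The trigger covers any death, and no link from these calls to the SRC is given.

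No section says who tells the SRC, by when, or from what moment the week runs.

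**Recording.** On the same class of events, 9.1.1 asks for no reporting, 9.2.1 requires an eCRF entry and 9.3 requires all AEs to be recorded. One could read 9.1.1 as meaning expedited reporting only, but it stands in the general AE section and does not say so.

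**Illustration of how many deaths could be involved.** Inputs: 27 Part B patients (10.2) and median survival of 6 to 9 months (1.1), extended by assumption to 24 months because 1.1 ties its figure to a historical lack of effective treatment. Assuming exponential survival from the start of treatment, expected deaths within 12 months are 27 × (1 − 2^(−12/m)), with m the median in months:

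- m = 6: 27 × 0.750 = 20.2
- m = 9: 27 × 0.603 = 16.3
- m = 12: 27 × 0.500 = 13.5
- m = 18: 27 × 0.370 = 10.0
- m = 24: 27 × 0.293 = 7.9

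These counts mix deaths on treatment with deaths in follow-up. The documents give neither the share that would be judged disease-related nor the rate of non-serious grade 4 events.

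**The case against.** The strongest reply is that the trigger is not tied to the SAE form. The people who learn of a death or a grade 4 result sit on the SRC or send a delegate, RM-CTU is represented, 11.3.6 says toxicities are reviewed and graded as they emerge, and 9.3 has the SRC review safety data regularly. Many grade 4 events will also count as life-threatening or medically important and so travel by the 24-hour route unless called disease-related. This stands as far as it goes: informal routes exist. None of them is a duty to notify or carries a deadline.

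Four stronger readings are tempting, and the documents do not support them.

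- A reader might infer that the trigger often cannot fire. Any SRC member can raise an event, and how often the formal route would fail cannot be computed from the documents.
- A reader might infer that a site may properly keep such events from the SRC. Section 9.2.1 waives the SAE form only and still requires the eCRF record, and 6.7.2 requires the meeting independently of section 9.
- A reader might infer that the protocol expects RAF inhibition in general to drive pathway hyperactivation, so that the exemption would hide drug-induced progression. Section 1.1.1.4 says this of selective mutant-BRAF inhibitors, and 1.1.1.5 argues that inhibiting both BRAF and CRAF prevents it. Section 9.1.1 also makes a suspected drug contribution to progression an AE, so only an unsuspected contribution could slip through.
- A reader might infer that Part A is defective for lacking the one-week trigger. It has weekly review in the first two cycles, a seven-day gap after the first patient in each cohort, usually fortnightly calls and provision for urgent safety measures. Extending the trigger is a design preference; what is missing is a statement of whether it applies.

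**Conclusion.** The point holds as a conflict between rules. An attribution-blind, one-week safeguard depends on a reporting system that filters by attribution and seriousness, and for disease-attributed events and non-serious grade 4 events no written route meets the limit. Separately, 9.1.1 contradicts 9.2.1 and 9.3 on whether disease-related events are captured at all.

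The defect goes beyond missing detail, because stated exemptions work against a stated safeguard and against the safety tables of a primary endpoint. Its frequency is unknown. The range of about 8 to 20 deaths among 27 patients within 12 months only illustrates that trigger events will not be rare. It rests on exponential survival and an assumed median of 24 down to 6 months, and it does not estimate missed events. The conclusion on deaths also rests on reading the 9.2.1 exemption as covering fatal disease-related events, which is plausible but not explicit.

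**What to change.** 1. In 6.7.2 and 9.2, require sites to notify RM-CTU within 24 hours, on the existing SAE form, of every grade 4 event and every death covered by the trigger, whatever the attribution. Keep the 9.2.1 exemption for regulatory expedited reporting only.
2. Name RM-CTU as the body that convenes the SRC on receipt, with the week starting then. The meeting would fall at most 1 + 7 = 8 days after the site learns of the event.
3. State in 6.7.2 which deaths count: for example those on treatment and up to 28 days after the last dose, or those in survival follow-up as well. The trigger and the notification duty must cover the same deaths. The narrower choice restricts the present wording, so it should be made openly.
4. Delete or reword the 9.1.1 sentence so that disease-related AEs are recorded as 9.2.1 and 9.3 require.
5. State whether the one-week trigger applies in Part A.

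The cost is protocol wording, a few extra notifications on a form already in use and some additional SRC teleconferences. Including survival follow-up would add the most meetings; stopping at 28 days after the last dose would keep the number lower.

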6.8 Dose escalation decisions

An SRC meeting will be triggered when three patients have had the opportunity to complete the first cycle of treatment. The safety data including a list of DLTs and all AEs will be reviewed, along with all other available data (including PK analyses from at least two subjects), in order to make the decision. When sufficient data are available to assess the existing cohort, the next dose level will be assigned according to the following:

- Proceed with dose escalation: If the data is available from three patients who have been treated in a cohort and no DLTs have been observed at that dose level, then dose escalation can be considered.
- Expand the cohort to further explore the dose level: If the data is available from three patients who have been treated in a cohort and one DLT has been observed at that dose level, then the cohort will be expanded to include six patients.
- De-escalate the dose: If two DLTs have been observed at any dose level, the dose will be de-escalated to either the previous dose level (expanding to include up to six patients) or an intermediate dose level will be explored. If the previous dose level already included a cohort of six patients then this will be identified as the MTD.
- Explore different dosing schedules or formulations: If the daily continuous dosing treatment schedule is not tolerated, then the frequency of dosing for subsequent patients may be reduced. Dose escalation will continue at the reduced schedule.
- Stop the dose escalation phase of the study.

The decisions of the SRC on the next dose level and/or dosing schedules will be documented and provided to the Investigators prior to dosing any new patients.

The RP2D to be further evaluated in Part B (expansion phase) will be determined by the SRC based on the MTD and observed safety profile, PK and PD data. During the expansion phase, the SRC will continue to monitor safety and will agree any action needed to refine the dose or dosing schedule.

6.8.1 Intra-patient dose escalation

Patients without disease progression or significant toxicity will be eligible for intra-patient dose escalation, which may occur at the end of every second treatment cycle, after at least 56 days on treatment. Such escalation would occur in addition to the three newly recruited patients allocated to the new dose level cohort, as long as at least 28 days of safety data was available for that dose level and the dose level had not been closed due to toxicity.

The decision of intra-patient dose escalation for each patient will be fully discussed and decided by the SRC. Those patients who have a dose escalation can be counted by the SRC for the purpose of considering further escalations. Additional PK samples will be collected from patients that have dose escalation at C2 D1 of the escalated dose regimen.

6.9 Dose modifications

6.9.1 Dose reductions

The dose of CCT3833 will be reduced to the previous dose level for any patient who experiences a DLT (which can occur during any cycle of treatment). Once the dose has been reduced, it should not be re-escalated. If any patient requires more than two dose reductions, the patient should be withdrawn from the study by the Principal Investigator.

6.9.2 Dose delays

If at the time of the scheduled start of the next cycle, any drug-related toxicities are still present and have not resolved to Grade 1 or to meet the eligibility criteria treatment should be delayed for up to 2 weeks until these toxicities have resolved to Grade 1 or to meet the eligibility criteria. If there is no recovery after a 2-week delay, the patient should be withdrawn from the study. In addition, a treatment delay of more than 28 days for reasons other than drug-related AEs will result in the patient being removed from the study.

6.9.3 Dose expansion cohort

Once a MTD is defined in Part A, Part B, the melanoma-specific expansion phase will begin at the defined RP2D in order to define the safety, tolerability, pharmacokinetics and pharmacodynamics and provide preliminary efficacy information on CCT3833.

Patients with metastatic or locally advanced (unresectable) melanoma will be recruited into clinically and molecularly defined groups (approximately 9 in each), namely:

1. BRAF mutant, BRAF inhibitor 'treatment naïve'.

2. BRAF mutant, with progression on licensed BRAF inhibitor.
3. RAS mutant.

The total number of patients in this stage of the study will therefore be 27. Recruitment to cohorts will take place simultaneously rather than sequentially. This stage of the study will again operate at two sites, namely the Royal Marsden Hospital, London, and The Christie Hospital, Manchester.

Melanoma patients treated at the RP2D in the dose escalation phase of the study may continue on study treatment if re-screening confirms their eligibility. They can therefore be included in the efficacy analysis in the expansion stage of the study, in addition to, the 9 patients in the relevant cohort.

Melanoma patients treated at a dose escalation dose other than the recommended Phase 2 dose, who remain on treatment at the time of commencement of Part B, may also be re-screened and, if eligible, resume treatment at the RP2D as part of the expansion stage. Again, these patients will be recruited in addition to, the 9 patients in the relevant cohort.

Any melanoma patient identified with PD on CCT3833, who has not previously received licensed BRAF inhibitor therapy (i.e. Cohort 1), will be immediately offered treatment with the most appropriate approved alternative targeted therapy. This 'rescue route' will ensure that a patient's treatment is not compromised through trial participation.

During the expansion phase, the SRC will continue to monitor safety and will agree any action needed to refine the dose or dosing schedule.

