Approximately 69 patients will be enrolled in this study in total, with up to 42 in Part A and approximately 27 in Part B. The total number of patients enrolled will depend upon the number of screen failures, number of dose escalations necessary, and number of evaluable patients.

The trial is expected to be open to recruitment for approximately 30-36 months. Patients will receive treatment with CCT3833 until disease progression or failure to tolerate treatment. It is anticipated that patient follow-up for survival status will be performed for up to 12 months after the last dose in Part B.

Table 4 Trial schematic

Number of patients and sites		Patient numbers per cohort		
Part A:	• n = up to 42	• n = 3-6		
Dose	• Sites:			
Escalation	○ DDU, RM Sutton			
	○ CTU, The Christie, Manchester			
Part B:	• n = 27 at RP2D	• BRAF mutant, BRAF inhibitor treatment naïve	• BRAF mutant with progression on BRAF inhibitor	• RAS mutant
Expansion	• Sites:	• N=9		• N=9
	○ RM Chelsea			
	○ CTU, The Christie, Manchester			

- N=9

RP2D = recommended Phase 2 dose

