8.2 Part B (dose expansion stage)

8.2.1 Pre-treatment evaluations

8.2.1.1 Baseline evaluations

The following must be performed/obtained between Day -28 and Cycle 1 Day 1:

- Written informed consent.

- Demographics.
- Medical history.
- Availability of historical tumour biopsy (for confirmation of mutation status).
- Height and ECOG performance status.
- Recording of symptoms.
- Review of concurrent medications.
- Echocardiogram (within 28 days of Day 1).
- Radiological imaging (within 28 days of Day 1).
- Tumour biopsy – optional.

The following must be performed between Day -7 and Cycle 1 Day 1:

- Physical examination.
- Clinical disease assessment (if applicable).
- Performance status, weight and vital signs.
- Laboratory investigations: including full blood count, APTT, PT, urea, sodium, potassium, creatinine, ALT, AST, albumin, total protein, total bilirubin, alkaline phosphatase, calcium, LDH, creatine kinase, ESR, CRP, glucose, HbA1c, troponin I, magnesium and phosphate, tumour markers (as appropriate).
- Urinalysis (bHCG).
- ECG.

Baseline imaging must document all areas of disease present (even if specific lesions are not going to be followed for response) and the measurements of all measurable lesions must be recorded clearly. Any non-measurable lesions must be stated as being present. For clinical measurements, documentation by colour photography, including a ruler to estimate the size of the lesion, is strongly recommended.

All radiological assessments must be performed between Day -28 and before starting treatment. The interval between the last anti-cancer therapy and these measurements must be at least 28 days. All clinical measurements to assess response must be done within 7 days before the patient starting treatment. Tumour lesions that are situated in a previously irradiated area can be included as measurable disease if they are clearly progressing at the time of initiating systemic therapy.

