10.2 Sample size

The sample size for this Phase 1 trial is not based on a formal sample size calculation as no formal statistical hypothesis is being tested. The total number of patients has been based on the desire to obtain adequate tolerability, safety, pharmacokinetic and pharmacodynamics data while exposing as few patients as possible to the IMP and procedures. The total number of patients required will depend upon the toxicities encountered and the number of dose cohorts required.

In Part A, the minimum number of patients will be 3, if there are 2 DLTs at the starting dose. The maximum number of patients is expected to be 42.

In Part B, there are 3 different patient cohorts each including 9 recruited patients, leading to a maximum of 27 patients within the expansion phase. An additional small number of patients from Part A may continue on treatment into Part B if they meet the inclusion criteria. These patients will be in addition to the 27 new patients recruited to Part B.

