10.3.3 Pharmacokinetics

PK parameters will be derived from sample data, including peak plasma concentration (C_{max}), time to reach C_{max} (T_{max}), elimination half-life ($T_{1/2}$), area under the curve from zero to the time of last quantifiable concentration (AUC_{0-t}) and AUC extrapolated to infinite time (AUC_{∞}). In addition, comparison between single dose and multi-dose PK parameters will be made for assessment of steady-state drug accumulation.

Bioanalysis will be performed by Covance UK. PK samples will be analysed for all patients in Part A, with a minimum of 2 patients/cohort analysis available to inform the assessment of patient safety and dose reviews.

The Correlation between the PK parameters derived and DLT or non-DLT toxicity at each dose level. Calculation of a correlation coefficient will determine the significance.

10.3.4 Response evaluation:

The best tumour response evaluation as determined radiologically or clinically will be presented as proportions. Part A and B patients undergo response assessment every 8 weeks (2 cycles), the first response assessment is therefore at 8 weeks, and they continue after that at 8 weekly intervals unless there is clinically measurable progression or toxicity. The association of the pharmacodynamics biomarkers with treatment response will be explored.

10.3.5 Expansion cohorts (Part B):

The tolerability, PD parameters and tumour response data will be evaluated as stated above for each melanoma cohort separately.

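### Melanoma patients carried over from Part A may be pooled into the Part B cohort estimates, although they were selected for not having progressed and having tolerated the drug

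*Combined protocol and SAP*

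**What the plan says.** Section 6.9.3 gives Part A melanoma patients two ways into Part B.

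- **Treated at the RP2D.** They "may continue on study treatment if re-screening confirms their eligibility". The section then states: "They can therefore be included in the efficacy analysis in the expansion stage of the study". They come on top of the nine in the relevant cohort.
- **Treated at another dose.** Those "who remain on treatment at the time of commencement of Part B, may also be re-screened and, if eligible, resume treatment at the RP2D", again on top of the nine. The text places them in the expansion stage but does not mention the efficacy analysis.

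Section 10.2 repeats that a few Part A patients may be added to the 27 new ones. Exclusion criterion 1 in section 4.3 allows prior CCT3833 for patients coming from Part A.

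On analysis, section 10.3.5 says: "The tolerability, PD parameters and tumour response data will be evaluated as stated above for each melanoma cohort separately". Section 10.3 lists safety and tolerability as a primary endpoint in both parts and response as a secondary one. Appendix 5 counts best overall response from the start of treatment. Section 8.2.1.1 requires new imaging within 28 days of Day 1 and adds: "The interval between the last anti-cancer therapy and these measurements must be at least 28 days". Nothing says which baseline applies to a carried-over patient, or that new and carried-over patients are to be shown apart.

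**The concern.** A Part A patient stays on CCT3833 only without progression and while tolerating it (section 2.1), and while still benefiting (section 6.11). Re-screening then reapplies the performance-status and organ-function criteria. Comparable melanoma patients who progressed early or stopped for toxicity have no such route into Part B. Membership of the carried-over group therefore depends on the outcomes that Part B is meant to describe.

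Section 2.1 gives Part B the purposes of further defining tolerability and safety and supporting the design of later trials. In a cohort of nine, one or two selected patients can visibly move a proportion. The wording is also permissive, so in an open-label trial the choice to include them could be made after their outcomes are known.

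**Working it through.** **1. The plan's own figures.** 3 cohorts × 9 = 27, matching "leading to a maximum of 27 patients within the expansion phase". 42 + 27 = 69, matching the total in section 2.1 ("with up to 42 in Part A and approximately 27 in Part B"). There is no power or alpha to reproduce: "The sample size for this Phase 1 trial is not based on a formal sample size calculation as no formal statistical hypothesis is being tested".

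**2. Inputs for the bias.** Nine new patients per cohort is from the protocol. The rest is assumed, because the documents do not give it: the number carried over per cohort, k = 1 to 3; the true response rate in new patients, p; and the response probability counted for a carried-over patient, q.

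**3. Expected pooled response rate** = (9p + kq)/(9 + k). With p = 15%:

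| k | q = 0 (re-baselined, no new response) | q = 40% | q = 60% |
|---|---|---|---|
| 1 | 13.50% | 17.50% | 19.50% |
| 2 | 12.27% | 19.55% | 23.18% |
| 3 | 11.25% | 21.25% | 26.25% |

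For k = 2: (1.35 + 0.8)/11 = 19.55%, (1.35 + 1.2)/11 = 23.18%, and 1.35/11 = 12.27%. The last two columns fit counting from the Part A start. The q = 0 column is the extreme case of a fresh baseline, where tumours that have already shrunk show no further response.

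**4. Tying q to the selection.** Suppose all responders and a share s of non-responders are still on drug. Then q = p/(p + (1 − p)s). With p = 20% and s = 0.25, q = 0.2/(0.2 + 0.2) = 50%. For k = 2 the pooled rate is (1.8 + 1.0)/11 = 25.5%. It is 22.4% for s = 0.5, 29.4% for s = 0.1, and 20% for s = 1 (no selection).

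As a marker only, since the plan sets no threshold, take the chance of three or more responses at p = 20%:
- nine new patients: 26%
- eleven unselected patients: 38%
- nine new plus two carried over at q = 50%: 56%

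The step from 26% to 38% comes from having two more patients. The step from 38% to 56% comes from selection.

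**5. Early intolerance.** Let the true rate in new patients be t and, as the bounding case, zero in carried-over patients. The pooled rate is 9t/(9 + k).

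| t | k = 1 | k = 2 | k = 3 |
|---|---|---|---|
| 10% | 9.0% | 8.2% | 7.5% |
| 20% | 18.0% | 16.4% | 15.0% |
| 33% | 29.7% | 27.0% | 24.8% |

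**6. Precision.** Exact 95% intervals are 3% to 60% for 2/9 and 11% to 69% for 4/11 (the same two responders plus two carried-over responders).

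**The case against.** The strongest reply is that Part B is descriptive. No hypothesis is tested, response is secondary, no response threshold is set, and the MTD and RP2D come from Part A alone. The nine new patients stay identifiable and could be reported alone. Part A tabulates toxicity by dose level and reports response, so patients who progressed or stopped there are not lost to the trial. Few are likely to carry over, since Part A takes all solid tumours at three to six evaluable patients per level. The shifts above are small against the confidence intervals. All of this stands and limits the severity. It does not remove the bias, because nothing requires the nine to be reported alone.

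Several stronger readings are tempting, but the documents do not support them.

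- **That pooling must inflate response.** The direction depends on an unstated baseline. Appendix 5 points to inflation. The imaging required by section 8.2.1.1 could become a new baseline, and the measurable-disease criterion in section 4.2.2 could keep out a complete responder. Either works the other way.
- **That all carried-over patients are expressly in every analysis.** Inclusion in the efficacy analysis is explicit only for RP2D patients. For other doses, and for tolerability, it is inferred from sections 6.9.3 and 10.3.5.
- **That the baseline is unattainable.** Exclusion criterion 1 permits prior CCT3833. What remains is that the imaging interval in section 8.2.1.1 has no matching exception.
- **That a Cohort 1 patient who has had CCT3833 is no longer treatment-naive.** The rescue provision in section 6.9.3 describes Cohort 1 by prior licensed BRAF inhibitors, which CCT3833 is not. Section 1.2.2 is looser, but that is a separate matter of definition.

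**Conclusion.** The concern holds as a bias in descriptive cohort estimates and should be fixed. It does not threaten a type I error rate or the dose decision. Following the plan as written can mix outcome-selected patients into cohorts of nine. Early tolerability and disease control would then look better than in newly treated patients. Response would be overstated if counted from the start of Part A and could be understated after re-baselining.

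The size cannot be derived from the documents. It rests on the assumed k, p and q above and is zero if nobody carries over. For two carried-over patients and a true response rate of 15%, the range runs from 12% to 23%. A true early-intolerance rate of 20% would read no lower than 16.4%.

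**What to change.** In sections 6.9.3 and 10.3.5, state that each cohort's response and tolerability estimates use newly recruited patients only. List carried-over patients separately, by Part A dose, with the baseline used for them stated.

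Reconcile the 28-day imaging interval in section 8.2.1.1 with the permission in section 6.9.3 and exclusion criterion 1 for patients to continue from Part A.

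If pooling is wanted, make it a labelled secondary analysis. It should take all melanoma patients who started at the RP2D in Part A and have known qualifying mutation status, from first dose and original baseline, whether or not they are still on treatment. Section 8.1.1.1 already collects a RECIST baseline in Part A.

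The main change is wording, and carried-over patients keep their access to treatment. The cost is a few patients fewer in each cohort estimate. The secondary analysis is limited to those whose mutation status is available, because section 2.1 does not mandate testing in Part A.
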